5.4. Administration

5.4.1. Administration of the Premedication

Premedication is required for all patients.

Patients will be pre-medicated with acetaminophen 650 mg orally and diphenhydramine 50 mg orally or intravenously 1 hour prior to GO dosing and 1 mg/kg methylprednisolone or an equivalent dose of an alternative corticosteroid within 30 minutes prior to infusion of GO (given prior to GO infusion may ameliorate infusion-related symptoms).

Follow standard practice of the institution to prevent tumor lysis syndrome.

Vital signs should be monitored during infusion and for 2 hours following infusion.

5.4.2. Administration of GO

Three doses of GO 3 mg/m² (up to one vial per dose) will be administered at investigational site as a 2-hour intravenous infusion after premedication on Days 1, 4, and 7 at each cycle. Patients will receive 1 or 2 cycles of GO. The second cycle of GO will be allowed at the investigator's discretion for patients who meet selected dosing criteria after the first cycle. (see [Section 7.5](#)).

Use appropriate aseptic technique for the reconstitution and dilution procedures. Protect the reconstituted and diluted GO solution from light. See the IP manual for instructions on how to administer GO.

5.4.3. Dosage Modification for Toxicities

- Every effort should be made to administer study medication on the planned dose and schedule. Patients are to be instructed to notify investigators at the first occurrence of any adverse symptom. In the event of multiple toxicities, dose modification should be based on the worst toxicity observed.
- Full recovery from hematologic toxicities is not a requirement for administration of the second or third dose on Day 4 or 7, respectively.

- In the event of non-hematologic toxicities, dosing may be delayed, omitted or discontinued as described below (Table 3) by monitoring chemistries especially total bilirubin, AST, ALT, and other severe or life-threatening non-hematologic toxicities through recovery from treatment-related toxicities.
- In the event of persistent hematologic toxicities after Cycle 1, conditional Cycle 2 dosing may be delayed or discontinued as described below (Table 3) by monitoring blood counts through recovery from treatment-related toxicities.

Table 3. Dosage Modifications for Non hematologic and Hematologic Toxicities

Non-hematologic Toxicities	Recommended Actions
VOD/SOS	
 • Discontinue GO.
Total bilirubin greater than $2 \times$ ULN, or AST and/or ALT greater than $2.5 \times$ ULN	
 • Delay treatment with GO until recovery of total bilirubin to less than or equal to $2 \times$ upper normal limit (ULN) and AST and ALT to less than or equal to $2.5 \times$ ULN prior to each dose. • Omit scheduled dose if delayed more than 2 days between sequential infusions.
Infusion-related reactions	
 • Interrupt the infusion and institute appropriate medical management. • Administer acetaminophen, diphenhydramine and/or methylprednisolone, if needed. • Provide supportive care measures as needed. • For mild, moderate or severe infusion related reactions, once symptoms resolve, consider resuming the infusion at no more than half the rate at which the reaction occurred. Repeat the procedure above in the event of recurrence of symptoms. • Permanently discontinue GO upon occurrence of a severe infusion reaction or for any life-threatening infusion reaction.
Other severe or life-threatening non-hematologic toxicities	
 • Delay treatment with GO until recovery to a severity of no more than mild (Grade ≤ 1). • Omit scheduled dose if delayed more than 2 days between sequential infusions.
Hematologic Toxicities	Recommended Actions
Persistent thrombocytopenia	
 • If platelet count does not recover to greater than or equal to $50,000/\mu\text{L}$ within 42 days after the last dose of GO in the first cycle, DO NOT administer the 2nd cycle.*
Persistent neutropenia	
 • If neutrophil count does not recover to greater than or equal to $1,000/\mu\text{L}$ within 42 days after the last dose of GO in the first cycle, DO NOT administer the 2nd cycle.*

* except in patients with the bone marrow blasts $\geq 5\%$, the decrease in neutrophils and platelets thought to be due to the underlying leukemia.

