8.3. Severity Assessment

If required on the AE page of the CRF, the investigator will use the adjectives MILD, MODERATE, or SEVERE to describe the maximum intensity of the AE. For purposes of consistency, these intensity grades are defined as follows:	
MILD	Does not interfere with subject's usual function.
MODERATE	Interferes to some extent with subject's usual function.
SEVERE	Interferes significantly with subject's usual function.

Note the distinction between the severity and the seriousness of an AE. A severe event is not necessarily an SAE. For example, a headache may be severe (interferes significantly with the subject's usual function) but would not be classified as serious unless it met one of the criteria for SAEs, listed above.

Investigators should report AEs using concise medical terminology (verbatim) as well as collect on the CRF the appropriate Common Terminology Criteria for Adverse Events (CTCAE) (Version 4.03, Publish Date: 14 June 2010, NCI CTCAE) listed in the Cancer Therapy Evaluation Program. New protocols of projects that have been utilizing a previous version may continue to use that version.

If required on the AE page of the CRF, the investigator will use the following definitions of severity in accordance with the current CTCAE version to describe the maximum intensity of the adverse event.

Grade	Clinical Description of Severity
0	No change from normal or reference range (This grade is not included in the Version 4.03 CTCAE document but may be used in certain circumstances.)
1	MILD adverse event
2	MODERATE adverse event
3	SEVERE adverse event
4	LIFE-THREATENING consequences; urgent intervention indicated
5	DEATH RELATED TO adverse event

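### Table 3 tells sites both to consider resuming and to permanently stop GO after a severe infusion reaction

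*Protocol*

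**What the plan says.** Protocol Section 5.4.3, Table 3, sets the action for each non-hematologic toxicity. For infusion-related reactions, the site first interrupts the infusion and gives medical management and supportive care. Two further bullets then decide whether GO continues.

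- Resume bullet: "For mild, moderate or severe infusion related reactions, once symptoms resolve, consider resuming the infusion at no more than half the rate" used before the interruption. It adds: "Repeat the procedure above in the event of recurrence of symptoms".
- Stop bullet, immediately below: "Permanently discontinue GO upon occurrence of a severe infusion reaction or for any life-threatening infusion reaction".

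A general rule above the table reads: "In the event of multiple toxicities, dose modification should be based on the worst toxicity observed". Protocol Section 8.3 grades adverse events by CTCAE. Grade 3 is severe, and Grade 4 is described separately as "LIFE-THREATENING consequences; urgent intervention indicated".

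**The concern.** The word *severe* appears in both bullets, and the two actions are incompatible. An investigator managing a severe reaction that has resolved finds one line that lets the infusion restart and another that ends GO treatment for that patient.

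Patient safety is at stake. A site relying on the resume bullet could restart GO in a patient whom the next line says must receive no more. The recurrence sentence has no severity limit and no cap on repeats, so this could happen more than once. If the stop bullet is not applied, the later scheduled doses follow by default, because Section 5.4.3 asks sites to keep to the planned dose and schedule as far as possible. The row applies equally to adults and to the 12-17 year olds.

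There is a smaller consequence for reporting. SAP Section 6.5.2 summarizes potentially important protocol deviations by category, and the present text does not settle whether resuming after a severe reaction is a deviation.

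**Working it through.** No statistical calculation applies. The check sets the two bullets against the severity scale and then looks for text that would reconcile them.

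**Step 1: map each grade to its instruction** (Table 3 against Section 8.3).

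| Severity | Resume bullet | Stop bullet | Result |
|---|---|---|---|
| Grade 1, mild | applies | no | resume only |
| Grade 2, moderate | applies | no | resume only |
| Grade 3, severe | applies | applies | conflict |
| Grade 4, life-threatening | no | applies | stop only |

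The overlap is exactly Grade 3. Section 8.3 does not subdivide *severe*, so the bullets cannot be read as covering different kinds of severe reaction. Table 3 itself links its adjectives to the grades: the row for other toxicities equates mild with Grade 1 or lower.

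**Step 2: try a first-versus-recurrent reading.** Under this reading, the resume bullet would cover a first severe reaction and the stop bullet a repeat. The text does not support it. The stop bullet is triggered by occurrence. Recurrence is dealt with inside the resume bullet, where the instruction is to repeat the procedure.

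**Step 3: look for a rule of precedence elsewhere.**

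- The worst-toxicity rule in Section 5.4.3 applies when there are several toxicities. It does not choose between two actions for one reaction of one grade.
- The Table 3 row headed "Other severe or life-threatening non-hematologic toxicities" covers other toxicities, not infusion reactions.
- Protocol Section 6.3 lists generic, investigator-determined reasons for stopping treatment and has no rule for infusion reactions.
- Protocol Sections 5.4.1 and 5.4.2 cover premedication and administration and set no precedence.
- SAP Sections 3.5.1.1 and 6.6.1 and Appendix 2 define and summarize infusion reactions as an adverse event of special interest. They give no dosing rule.

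**Step 4: count the infusions the row governs.**

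- Patients: 50 adults + 6 pediatric = 56 (Protocol Section 3).
- Cycle 1: 56 × 3 doses = 168 planned infusions.
- Two cycles: 56 × 6 doses = 336. This is a ceiling, because Cycle 2 is conditional and at the investigator's discretion.

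These figures show how widely the row applies. They do not estimate how often the conflict will arise.

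**The case against.** The strongest reply is that a safe reading is available. The resume bullet only invites the site to consider restarting, while the stop bullet is a direct instruction, comes last and is specific to severe and life-threatening reactions. A site that stops complies with both. The column is headed as recommended actions, so calling the other course a breach may be somewhat strong. That reading is indeed the safer one, but the protocol does not say that it prevails, and naming severe reactions in the resume bullet gives express permission to restart.

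A second reply is that the resume bullet concerns only the interrupted infusion and does not itself authorize later doses. This is fair: the extension to later doses is an inference from the default schedule, not something the bullet states. The conflict over the interrupted infusion is there on the face of the text.

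Third, there are safeguards. Premedication is required, vital signs are monitored during the infusion and for 2 hours afterwards, study staff give every dose at the site, patients with a history of allergic reactions to similar compounds are excluded, and resuming depends on symptoms having resolved. The investigational product manual, which is not among the documents, may also say more. These points bear on how likely harm is. They do not remove the inconsistency from the protocol.

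**Conclusion.** The concern holds. Table 3 assigns Grade 3 infusion reactions to two incompatible actions, and neither document says which governs. The conflict is confined to that one grade but can arise at any of the 168 planned Cycle 1 infusions and at any Cycle 2 infusion. How often it would arise cannot be stated, since the documents give no rate of severe infusion reactions and none is assumed here.

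The conclusion rests on reading *severe* in Table 3 as Grade 3 in Section 8.3, and on the protocol and SAP text alone. It should be corrected because, followed as written, the resume bullet permits re-exposure that the next bullet forbids. It does not touch the primary QTcF analysis, the 20 msec margin or the sample size.

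**What to change.** Make exactly one instruction apply to severe reactions.

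- **Default:** limit the resume bullet to mild or moderate reactions by deleting severe from it. Leave the stop bullet as it is for severe and life-threatening reactions.
- **If the clinical team intends to allow rechallenge after a first severe reaction:** change the trigger in the stop bullet from occurrence to recurrence of a severe reaction, keep permanent discontinuation for any life-threatening reaction, and limit the repeat-the-procedure sentence to mild or moderate recurrences.

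The choice between the two is clinical. The default is the more cautious and keeps the stop rule already written.

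Either change needs a short protocol amendment or a clarification letter to sites, with a check that the investigational product manual agrees. Under the default, a few patients may miss later doses and the ECGs tied to them. The analysis does not change.

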5.5. Investigational Product Storage

The investigator or an approved representative, eg, pharmacist, will ensure that all investigational products are stored in a secured area with controlled access under required storage conditions and in accordance with applicable regulatory requirements.

Investigational products should be stored in their original containers and in accordance with the labels.

See the investigator product manual for storage conditions of the product once reconstituted and/or diluted.

Any storage conditions stated in the SRSD will be superseded by the storage conditions stated on the product label.

Site systems must be capable of measuring and documenting (for example, via a log), at a minimum, daily minimum and maximum temperatures for all site storage locations (as applicable, including frozen, refrigerated, and/or room-temperature products). This should be captured from the time of investigational product receipt throughout the study. Even for continuous-monitoring systems, a log or site procedure that ensures active evaluation for excursions should be available. The intent is to ensure that the minimum and maximum temperature is checked each business day to confirm that no excursion occurred since the last evaluation and to provide the site with the capability to store or view the minimum/maximum temperature for all non-working days upon return to normal operations. The operation of the temperature monitoring device and storage unit (for example, refrigerator), as applicable, should be regularly inspected to ensure they are maintained in working order.

Any excursions from the product label storage conditions should be reported to Pfizer upon discovery. The site should actively pursue options for returning the product to the storage conditions described in the labeling, as soon as possible. Deviations from the storage requirements, including any actions taken, must be documented and reported to Pfizer.

Once an excursion is identified, the investigational product must be quarantined and not used until Pfizer provides permission to use the investigational product. It will not be considered a protocol deviation if Pfizer approves the use of the investigational product after the temperature excursion. Use of the investigational product prior to Pfizer approval will be considered a protocol deviation. Specific details regarding information the site should report for each excursion will be provided to the site.

Receipt of materials, door opening and closing, and other routine handling operations where the products are briefly out of the temperature range described in the labeling are not considered excursions.

5.6. Investigational Product Accountability

The investigator site must maintain adequate records documenting the receipt, use, loss, or other disposition of the investigational product supplies. All investigational products will be accounted for using a drug accountability form/record.

5.6.1. Destruction of Investigational Product Supplies

The sponsor or designee will provide guidance on the destruction of unused investigational product (eg, at the site). If destruction is authorized to take place at the investigator site, the investigator must ensure that the materials are destroyed in compliance with applicable environmental regulations, institutional policy, and any special instructions provided by Pfizer, and all destruction must be adequately documented.

5.7. Concomitant Treatment(s)

All concomitant medications required to clinically manage patients while they are receiving GO therapy are permitted, including any palliative and supportive care for cancer related symptoms. Investigational drugs, anti-cancer therapy (except hydroxyurea as cytoreduction), and radiation (eg, cranial irradiation for CNS leukemia) are prohibited 2 weeks prior to study entry, during the GO treatment period, and before the determination of remission status by bone marrow (BM) assessment.

The patients treated with medications that are known to predispose to Torsades de Pointes should discontinue the drugs at least 2 weeks prior to enrollment. Medications that are known to cause QT prolongation should be avoided whenever possible during the GO treatment period and the post-GO period, but allowed after EOT visit. Refer to [Appendix 4](#) for assessing drugs known to predispose to Torsades de Pointes.

All concomitant medications, including prescription and nonprescription drugs, nondrug treatment, and dietary supplements and herbal preparations, will be entered on the case report form (CRF). Concomitant medications and treatments will be recorded from 28 days prior to the start of study treatment and up to 36 days post the last dose of study treatment or starting subsequent anticancer therapy (eg, consolidation or conditioning regimen).

6. STUDY PROCEDURES

The enrollment (study entry) day is defined as Day 1, when patient identifier is assigned with the first GO dosed.

6.1. Screening

Informed consent document (ICD) approved by an Institutional Review Board (IRB) or Independent Ethics Committee (IEC) must be signed and dated before any study-specific procedures are conducted. Screening procedures for evaluating eligibility and baseline data will be completed within 28 days prior to dosing on Day 1 unless otherwise noted.

The following will be collected at screening:

- Sign informed consent form and obtain documentation of assent at screening for those patients under age 18 (or as specified per local policy/laws).
- Review study eligibility (inclusion and exclusion criteria).

- Evidence of CD33 positivity for eligibility at screening, eg, by immunophenotyping of bone marrow or leukemia blasts in the peripheral blood performed by local laboratory using a validated assay and obtained within 28 days of enrollment will be collected and recorded in the CRF. Surface CD33 expression should be measured by flow cytometry (flow-activated cell sorting, FACS); immunohistochemistry (IHC) analysis is allowed in patients with (1) dry tap; or (2) if BM specimen is inadequate and/or with insufficient circulating blasts for FACS. **CCI**

- Medical history: To be collected within 28 days prior to first dose.
 - Chronic conditions and/or medical history of significance including alcohol use and relevant radiation and surgical procedures;
 - Any other previous cancer diagnosis;
 - Patients with prior HSCT are allowed in the study but those with history of VOD/SOS are not allowed. Medical history must be reviewed for evidence of VOD/SOS (eg, weight gain, elevated bilirubin, tender hepatomegaly, and ascites may indicate underlying VOD/SOS), especially if a patient received high-dose chemotherapy followed by HSCT;
 - Current disease: Initial AML diagnosis, relevant information for conclusive morphologically documented, refractory or relapsed CD33-positive AML, Eastern Cooperative Oncology Group performance status (ECOG PS) will be assessed. (Definition of refractory and relapsed AML as per ELN 2017 recommendation,⁵ see [Appendix 5](#)).
- Focused physical examination performed with clinical judgment evaluating potential areas of AML relapse and any clinically significant abnormalities which may include the following body systems: general appearance, skin, head/eyes/ears/nose/throat, heart, lungs, testes, abdomen, extremities, neurological, back/spinal, and lymph nodes; including worsening of medical history conditions.
- Imaging Assessment: Patients with suspected extramedullary disease will have imaging assessment (eg, computed axial tomography [CAT] or magnetic resonance imaging [MRI]) of relevant sites.
- Vital signs including height, weight, blood pressure, pulse, and temperature. ECOG PS will also be assessed.
- Laboratory evaluations as described in [Section 7.4, Appendix 3](#), and [Schedule of Activities \(Table 1\)](#).

- For women of childbearing potential, a beta-human chorionic gonadotropin (β -hCG) urine or serum pregnancy test must be conducted as specified in [Section 7.7](#).
- ECG at screening will be collected in triplicate within 28 days prior to enrollment. The results will be read and interpreted at the investigational site for eligibility determination; results of QTcF assessment are to be available prior to enrollment.
- Patients may be enrolled following successful completion of the pre-study assessments, screening procedures, and confirmation of eligibility.
- Evaluations of HIV and hepatitis B serological tests and hepatitis C tests will be conducted (see [Appendix 2](#)).
- Adverse events should be documented and recorded using NCI CTCAE version 4.03 (see [Section 8](#)).

6.2. Study Period

The total study period at each cycle is comprised of following periods:

- GO Treatment: Starts with the first dose of GO (Day 1) and ends with the last dose of GO (usually Day 7).
- Post-GO Period: Starts on the day after the last dose of GO and ends on 36 days after the last dose of GO or start of subsequent anticancer therapy, including consolidation and/or conditioning regimen. This period ends with End-of-Treatment (EOT) visit.
- If the optional second cycle of GO is administered, the same GO Treatment and Post-GO Periods are repeated starting once when Cycle 1 remission status is determined. The second cycle must be started no later than 42 days after the last dose of GO. This period ends with End-of-Treatment (EOT) visit.
- Follow-up Period: Starts on the day after EOT visit and ends when a patient completes 12 months on the study or death, whichever occurs first. This is end of study for each patient.

6.2.1. GO Treatment

Each cycle includes an active GO treatment phase (Days 1, 4, and 7) and a post GO treatment phase (Day 10 to 21).

The second cycle is allowed at the investigator's discretion for patients who meet the following dosing criteria after Cycle 1 (refer also to [Table 3](#) describing hematologic toxicities): Bone marrow with a decrease of blast percentage to at least 25%, or a decrease of pretreatment blast percentage by at least 50%; **and** blood count with neutrophils $\geq 1,000/\mu\text{L}$ and platelets $\geq 50,000/\mu\text{L}$, except in patients with the bone marrow blasts $\geq 5\%$, the decrease in neutrophils and platelets thought to be due to the underlying leukemia.

Patients who don't meet these criteria after the first cycle of GO are not allowed to receive the 2nd cycle. Cycle 2 Day 1 must be started no later than 42 days after the last dose of GO (ie, Cycle 1 Day 7).

6.2.2. Cycle 1

6.2.2.1. Cycle 1 Day 1 (GO Treatment)

[figure not shown]
- On Day 1 patients may be admitted at the site for 24 hours for pharmacokinetic/pharmacodynamic (PK/PD) sampling at investigator's discretion. Hospitalization beyond Day 1 is per standard of practice and investigator judgment. If there is prolongation of hospitalization, consider if SAE criteria are met (see [Section 8.2.4](#)).
- Laboratory specimen will be collected per the [Schedule of Activities](#) (and assessed per [Section 7](#)). Results of complete blood counts, and serum chemistry tests must be checked before dosing. Patients will have a blood sample collected prior to GO administration for the measurement of immunogenicity (antibodies to GO [ADA] and neutralizing antibody [NAb]).

C
C
I

- Patients will be weighed for body surface area (BSA) calculation.
- Physical examination (PE) performed with clinical judgment evaluating potential areas of AML relapse and any clinically significant abnormalities which may include the following body systems: general appearance, skin, head/eyes/ears/nose/throat, heart, lungs, testes, abdomen, extremities, neurological, back/spinal, and lymph nodes; including worsening of medical history conditions.
- Vital signs including blood pressure, pulse, and body temperature will be performed prior to GO infusion and 2 hours after the infusion is complete (see [Table 1](#)). ECOG PS assessment will be conducted if acceptable screening assessment is not done within 7 days prior to the start of investigational drug.
- Pre-medication should be given before GO infusion. See [Section 5.4.1](#) and [Section 5.4.2](#) for administration of premedication and GO, respectively.
- Electrocardiograms (ECGs) will be collected in all patients according to [Schedule of Activities \(Table 2\)](#) and as described in [Section 7.1](#). The ECGs will be collected in triplicate (3 consecutive ECGs approximately 2 minutes apart). Predose ECGs will be performed prior to GO dosing, after administration of premedications. Triplicate ECGs will also be performed prior to selected serial PK draws, around the time when the C_{max} is expected and immediately before the end of the infusion, ie, prior to the Hour 2 PK sample collection (within 15 minutes).³

C
C
I

- Pharmacokinetic (all patients) 

[figure not shown]
PK collections will include predose (Hour 0),
Hour 1, 2, 4, 6, and 24 as described in [Schedule of Activities \(Table 2\)](#).  Adverse events
should be documented and recorded using NCI CTCAE version 4.03 (see [Section 8](#)).

- Concomitant medications and treatments will be recorded.

